The primary statistical test for the primary endpoint will be performed using a repeated measures mixed model with the baseline stratification factor (i.e., the prostanoid usage status) treatment arm, week and treatment-by-week as the fixed effects. As a covariate, baseline 6MWD assessment (defined by the average of two 6MWTs at Week 2 after the completion of the run-in phase) will be included in the model. In case the normality assumption is invalid, the primary efficacy endpoint will be analyzed using the van Elteren test stratified by the prostanoid usage status. Summary statistics will be provided for all study variables with descriptive statistics (number of observations, mean, standard deviation, median, minimum, maximum and from the analysis model the least squares means, SAE's and confidence limits) for numerical (or continuous) variables and with frequency and percentage for categorical variables.

Exploratory analyses will be performed to evaluate the effects of demographics and baseline characteristics on the efficacy response with appropriate statistical methods. Subgroup analyses based on study drug usage, background therapies, demographics and baseline characteristics, as well as other study compliance status will be conducted. Additional statistical methods such as mixed effects model and Cochran-Mantel-Haenszel (CMH) test (for dichotomized response analysis) may be utilized in the exploratory analyses.

Interim analyses will be conducted when data is available from 75 patients. The purpose of the interim analysis is to stop the trial early for efficacy or futility or to continue the trial to 150 or 188 patients (total randomized is higher to account for an anticipated 20% drop out rate). Group sequential early stopping criteria and sample size re-estimation methodology are further described in the statistics section of this protocol. They are constructed to control overall type 1 error at 0.025, 1-sided.

Simulations assuming true underlying mean treatment difference in 6MWD ranging from 30-70 meters and SD's from 50 to 75 meters yielded >87% power for all cases except the most extreme case (mean difference 30 meters and SD 75, for which power was ~71%.

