16.3. Efficacy Analyses

16.3.1. Primary Efficacy Endpoint

The primary endpoint is to evaluate the efficacy of iNO as measured by the placebo-adjusted change in 6-minute walk distance (6MWD) from baseline to 18 weeks. The average of the two 6MWDs at Week 2 (after run-in) will be used as the baseline value for analysis of data. The

6MWD at Week 2 should be obtained on all subjects, even if the subject does not qualify to enter into the treatment phase.

The primary statistical test for the primary endpoint will be performed using a repeated measures mixed model with the baseline stratification factor (i.e., the prostanoid usage status), - treatment arm, week, and treatment-by-week interaction as the main effects. As a covariate, baseline 6MWD assessment will be included in the model. In case the normality assumption is substantially violated (i.e., graphical assessment of residuals from the analysis model and the Shapiro-Wilk test statistic graphical assessment of the residuals from the analysis model and), the primary efficacy endpoint will be analyzed using the van Elteren test stratified by the prostanoid usage status. Least Squares mean differences, standard errors, 95% confidence intervals will be derived from the analysis model.

Exploratory analyses will be performed to evaluate the effects of demographics and baseline characteristics on the efficacy response with appropriate statistical methods. Subgroup analyses based on study drug usage, background therapies, demographics and baseline characteristics, as well as other study compliance status will be conducted. Additional statistical methods such as mixed effects model and Cochran–Mantel–Haenszel (CMH) test (for dichotomized response analysis) may be utilized in the exploratory analyses.

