### Missing Data Imputation Rules:

Missing data will not be imputed for primary analysis.

The results will be presented in terms of LS means and the difference between LS means, with associated confidence interval and p-value.

Standard descriptive statistics for two separate categories ((1) increase in 6MWD from baseline at Week 18 and decrease in 6MWD from baseline at Week 18) will be presented along with the visit-wise 6MWD.

This analysis will be performed on Intention to treat (ITT), Per-Protocol (PP) and Modified Intention to treat (mITT).

Analysis performed on ITT will be considered as primary.

The within-subject error is assumed to have an unstructured (UN) covariance matrix. However, if the fit of the unstructured (UN) covariance structure fails to converge, then the following options will be tried in order until convergence is reached.

- 1) Toeplitz with Heterogeneity (TOEPH)
- 2) Autoregressive with Heterogeneity (ARH(1))
- 3) Toeplitz (TOEP)
- 4) Autoregressive (AR(1))
- 5) Compound Symmetry (CS)

If model still doesn't converge then this will be highlighted and discussed in the BDR meeting and an appropriate covariance structure to be used will be agreed. The denominator degrees of freedom will be estimated using a Kenward-Roger approximation. The pairwise treatment differences will be estimated as differences between the least-squares means and tested using an F-test based on the Type III sums of squares.

The SAS code for the MMRM analysis is provided below for interim analysis.

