**PROC MIXED Data= 6MWD;**

**CLASS PATID TREAT STRATA VISIT;**

**MODEL CHG = 6MWDBASE TREAT STRATA VISIT TREAT\*VISIT / DDFM=KR OUTPRED=RESID;**

**REPEATED VISIT / SUBJECT=PATID (TREAT) GROUP = TREAT type=UN;**

**LSMEANS TREAT\*VISIT / PDIFF cl;**

**ODS OUTPUT DIFFS=DIFFS1;**

**ODS OUTPUT LSMEANS=LSMEANS1;**

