**RUN;**

If the blinded data is used to determine the sample size then Z statistics by CHW will not be used. This decision will be taken before interim analysis.

If the unblinded data is used to determine the sample size then Z statistics by CHW will be used.

For final analysis the Z statistics will be calculated using the CHW method (Cui L, Hung HM, Wang SJ, 1999).

If the sample size does not increase, the test statistics at the final analysis, denoted by  $Z_N$  is weighted sum of the test statistics from the two stages  $Z_n$  (Test statistics at interim) and  $Z_{N-n}$  ([Menon and Zinc](#)).

$$Z_N = \sqrt{\frac{n}{N}} Z_n + \sqrt{\frac{N-n}{N}} Z_{N-n}$$

If after interim analysis, the sample size is increased to M ( $M > N$ ) per group, the same statistic becomes: .

$$Z_M = \sqrt{\frac{n}{N}} Z_n + \sqrt{\frac{M-n}{M}} Z_{M-n}$$

This may inflate the type one error and hence CHW proposed a new test statistics as follows:

$$Z'_M = \sqrt{\frac{n}{N}} Z_n + \sqrt{\frac{N-n}{N}} Z_{M-n}$$

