### **Normality Assumption:**

Normality assumption for Change from baseline in 6MWD will be assessed using the following:

1. Shapiro-Wilk statistics and
2. Visual examination of Q-Q plots.

PROC UNIVARIATE procedure in SAS will be used to check for the normality assumption. The normal probability plot (normal Q-Q plot) of residuals will also be generated and used to assess the normality. If

the residuals generated come from normal distribution then the normal probability plots should approximate straight lines.

Following SAS code will be used to generate Wilk's Shapiro and Q-Q plots.

```
PROC UNIVARIATE Data= Residual  NORMAL;
VAR RESID;
QQPLOT RESID /NORMAL (MU=EST SIGMA=EST COLOR=RED L=1);
RUN;
```

Normality results will be discussed during model diagnostics post unblinding and analysis approach will be finalized.

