#### **Analysis of Non-Normal Data:**

In case of normality issues, the analysis will be performed using van Elteren test for stratified response (change from baseline).

The SAS code applied as follows:

```
Proc Npar1way data=data;
```

```
  Strata strata;
```

```
  Class treatment;
```

```
  Var change;
```

```
Run;
```

In case, we encounter normality issues, the results needs to be interpreted accordingly.

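### SAP 7.3.1 leaves the choice between MMRM and van Elteren for the primary 6MWD test to a discussion after unblinding, with no cut-off, so one-sided 0.025 control is not guaranteed

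*SAP*

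**What the plan says.** **Primary test.** SAP 7.3.1 analyses change in 6MWD by MMRM. SAP Table 25 labels one row as primary, MMRM on the ITT set, with no condition attached.

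**Fallback.** Three places name van Elteren as the replacement, each with its own trigger:
- Protocol synopsis: "In case the normality assumption is invalid, the primary efficacy endpoint will be analyzed using the van Elteren test".
- Protocol 16.3.1: "In case the normality assumption is substantially violated", followed by a garbled bracket that mentions graphical assessment and Shapiro-Wilk.
- SAP 7.3.1, Analysis of Non-Normal Data: "In case of normality issues, the analysis will be performed using van Elteren test for stratified response (change from baseline".

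**Who decides, and when.** SAP 7.3.1, Normality Assumption, lists Shapiro-Wilk and Q-Q plots, then says: "Normality results will be discussed during model diagnostics post unblinding and analysis approach will be finalized". The introduction to Protocol 16 says the SAP is to be final before treatment assignment is unblinded.

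**Residuals.** They come from the model "MODEL CHG = 6MWDBASE TREAT STRATA VISIT" plus the treatment-by-visit term, with `GROUP = TREAT` and subject nested in treatment. The normality code runs on all residuals, without restriction to Week 18.

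**Two-stage statistic.** The MMRM code is introduced with "The SAS code for the MMRM analysis is provided below for interim analysis". The CHW formula describes its first component as "Test statistics at interim", and SAP Table 35 applies the interim boundary to a Wald statistic. Together these point to the interim MMRM Z as stage 1. No sentence says whether that holds if van Elteren is triggered. The same section says CHW will not be used if blinded data set the sample size, and also that the final Z uses CHW.

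**The concern.** Naming two tests does not specify which one decides. With no number attached to the trigger, two careful statisticians could select different primary tests from the same data. As coded, the check needs treatment codes, and the decision is placed after unblinding, when both p-values can be known. If MMRM and van Elteren fall on opposite sides of the boundary, nobody could show afterwards that the choice was independent of the result. At stake is whether the one-sided 0.025 claim for the primary endpoint can be verified. The two secondary endpoints are also affected, because they are tested only if 6MWD succeeds.

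**Working it through.** **1. Is there a rule anywhere?** The synopsis, Protocol 16.3.1 and SAP 7.3.1 give three trigger wordings. None gives a Shapiro-Wilk cut-off, a Q-Q criterion, a rule for when the two diagnostics disagree, or a named decision-maker.

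**2. Do the stated boundaries leave any alpha spare?** Inputs from SAP Table 35 and SAP 8.0: gamma -3, interim at 75 of 150, equal weights.
- Interim spend: 0.025 × (1 − e^1.5)/(1 − e^3) = 0.025 × 3.4817/19.0855 = 0.00456 (stated 0.0046).
- The final critical value solves P(Z1 < 2.607, Zfinal < c) = 0.975 with correlation √0.5. This gives c = 1.998 and a nominal level of 0.02288 (stated 0.0229).

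Both boundaries reproduce. One test fixed in advance gives 0.0250 if the futility stop is ignored and 0.0225 if it is followed. No alpha is set aside for choosing between two tests.

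**3. Where does the futility stop fall?** Under the interim trend with equal stages, CP = Φ(2z − 1.997√2). At z = 1.732, 2.165, 2.309 and 2.598 this gives 0.739, 0.934, 0.964 and 0.991, as in SAP Table 22. CP = 10% falls at z = (−1.2816 + 1.997√2)/2 = 0.77, and about 78% of null trials lie below it. Only the CP arm of the futility rule is modelled.

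**4. Upper limit of the freedom left open.** Let M and V be the MMRM and van Elteren Z statistics in a stage, each standard normal under the null, with correlation ρ. The interim efficacy stop is on M1 at p < 0.0046. At the final analysis the more favourable test is always taken, at p < 0.0229:
- Stage 1 fixed: success if (M1 + max(M2, V2))/√2 > 1.997.
- Choice covering both stages: success if max[(M1 + M2)/√2, (V1 + V2)/√2] > 1.997.

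The documents do not give ρ, so 0.72-0.96 is assumed. Numerical evaluation at N = 150 gives:

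| Choice | Futility ignored, ρ = 0.96 to 0.72 | Futility followed, ρ = 0.96 to 0.72 |
|---|---|---|
| Stage 1 fixed | 0.029 to 0.036 | 0.026 to 0.031 |
| Both stages | 0.031 to 0.040 | 0.027 to 0.031 |

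**5. Cross-check by simulation.** This used 20,000 null trials per scenario (Monte Carlo SE about 0.0011) and two stages of 75, with no futility stop. Assumptions not in the documents: a Week 18 ANCOVA stands in for MMRM, 40% use prostanoids, the baseline-change correlation is 0 to −0.5, errors are normal, t5, t3 or skewed, and no data are missing.
- One test fixed in advance: 0.023-0.027.
- Mechanical switch at Shapiro-Wilk p < 0.05 on Week 18 residuals: 0.024-0.027.
- More favourable test at the final analysis, choice covering both stages: 0.029-0.041.
- The same, with the interim decision also open: 0.030-0.042.

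No figure is offered for discretion used only when Shapiro-Wilk rejects. The SAP tests residuals from all visits together, so the rejection rate depends on between-visit correlations that the documents do not give.

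**The case against.** The strongest reply is that both diagnostics and a single fallback are named in advance, that residuals are pooled across arms, and that a decision made on residuals alone stays near 0.025. That stands, and it is why the figures above are upper limits. It does not supply the missing rule.

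Table 25 lists MMRM as the only primary row, and van Elteren appears in neither Table 24 nor Table 25. This suggests that MMRM was meant to stay primary. It does not override Protocol 16.3.1 and the SAP's own section on non-normal data, which both substitute van Elteren. It does make the simplest repair easy.

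The contrast with the covariance structure should not be overdrawn. There, "the following options will be tried in order until convergence is reached", but if nothing converges the matter goes to discussion at the BDR meeting, a term the SAP does not expand. That choice is more closely ruled, not completely ruled.

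The trigger sentence in Protocol 16.3.1 is visibly broken, so an intended criterion may have been lost. None can be recovered from the text.

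The CHW combination is not certain either, because the SAP's statements on it conflict. The sizes above apply to the CHW branch.

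Two stronger readings are tempting. A reader might infer that the true error is 0.03-0.04, or that the plan lets the better p-value be picked. Nothing in the documents says the choice will follow the p-values. A reader might also count the ranked MMRM as a third candidate. Table 24 item 12 makes it a sensitivity analysis, so it is not one.

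**Conclusion.** The gap is real and should be closed before the interim unblinding. The primary test is left open with codes visible, no cut-off and three trigger wordings, against the protocol's own commitment to a SAP that is final before unblinding. This conclusion rests on the text and needs no simulation. One-sided 0.025 control is not guaranteed; it is not shown to be lost.

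The excess is modest: at most about 0.029-0.036 with stage 1 fixed as the interim MMRM Z, or 0.031-0.040 if the choice covers both stages. Following the futility stop lowers these to 0.026-0.031 and 0.027-0.031. The sizes rest on the assumed correlations of 0.72-0.96, the CHW combination, and an interim stop decided on MMRM. Confidence is high on the missing rule and lower on the exact figures.

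**What to change.** Before the interim unblinding, delete the sentence that finalizes the approach after unblinding, and adopt one of two rules.

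**Preferred.** State that MMRM is primary regardless of residual diagnostics, as Table 25 already lists it, and that van Elteren is a sensitivity analysis. Amend the synopsis, Protocol 16.3.1 and the SAP section on non-normal data to match. This needs a protocol amendment but no extra patients and no boundary change. The price is some power under strongly non-normal errors. In a simulation at 30 m and SD 60 m (Week 18 ANCOVA for MMRM, 20,000 trials per error shape, futility stop followed), power was 0.86 with normal errors and 0.86-0.88 with non-normal shapes. The largest loss against a switch at an example cut-off of p < 0.01 was 0.897 − 0.863 = 0.034, under exponential errors.

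**Alternative.** At a blinded data review, before codes are released, apply one numeric Shapiro-Wilk cut-off to pooled Week 18 residuals. The text must:
- take the residuals from a model with `TREAT`, `TREAT*VISIT`, `GROUP=TREAT` and the treatment nesting in `SUBJECT` all removed, since each needs codes;
- say that this replaces the graphical criterion in Protocol 16.3.1 and the all-visit check in SAP 7.3.1;
- say which test supplies each stage's Z under CHW;
- say which test is used if CHW does not apply;
- use the same trigger wording in the synopsis, Protocol 16.3.1 and SAP 7.3.1.

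This also changes a protocol criterion, so it is more than a clarification. In the same power simulation it gave 0.86 with normal errors and 0.86-0.91 otherwise.

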#### **Analysis of Non-Normal Data:**

In case of normality issues, the analysis will be performed using van Elteren test for stratified response (change from baseline).

The SAS code applied as follows:

```
Proc Npar1way data=data;
```

```
  Strata strata;
```

```
  Class treatment;
```

```
  Var change;
```

```
Run;
```

In case, we encounter normality issues, the results needs to be interpreted accordingly.

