16.2. Sample Size Determination

Interim Analysis will be conducted by an independent DMC after 18-week 6MWD data are available from 75 patients. The purpose of the interim analysis is to stop the trial for an early efficacy or futility conclusion or to continue the trial to 150 or 188 - patients (total randomized is higher to account for an anticipated 20% dropout rate). Group sequential early stopping criteria and sample size re-estimation methodology are further described in the statistics section of this protocol. They are constructed to control overall type 1 error at 0.025, 1-sided. Simulations assuming true underlying mean treatment difference in 6MWD ranging from 30-70 meters and standard deviations from 50 to 75 meters yielded >87% power for all cases except the most extreme case (mean difference 30 meters and SD 75), for which power was ~71%.

Subjects who do not comply with the required device adherence, as well as who do not meet the study entry criteria at Week 2, will be withdrawn from the study.

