This is the "promising zone" sample size re-estimation (SSR) design of Mehta & Pocock (2011), which uses the Cui, Hung, Wang (1999) method of analysis to combine the test statistics for the separate analyses of the IA and post-IA parts of the trial, if the trial does not stop at IA.

The final analysis is via weighted Z statistic using equal weights for the IA and post IA test statistics. It requires $p < 0.0229$ 1-sided for statistical significance to control the overall type 1 error level at 0.025 1-sided per the $\Gamma = -3$ error spending function (Hwang, Shih, deCani 1990).

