**Table 22: Conditional and Predictive Power**

S.D	Mean Difference	Interim Z Statistics	Conditional Power (CP)	Predictive Power (PP) with vague prior#	Predictive Power (PP) with informative prior*
50	30	2.598	0.991	0.951	0.994
	40	3.464	$>0.999$	0.998	$>0.999$
	50	4.33	$>0.999$	$>0.999$	$>0.999$
	60	5.196	$>0.999$	$>0.999$	$>0.999$
	70	6.062	$>0.999$	$>0.999$	$>0.999$
60	30	2.165	0.934	0.853	0.974
	40	2.887	0.998	0.981	0.998
	50	3.608	$>0.999$	0.999	$>0.999$
	60	4.33	$>0.999$	$>0.999$	$>0.999$

S.D	Mean Difference	Interim Z Statistics	Conditional Power (CP)	Predictive Power (PP) with vague prior#	Predictive Power (PP) with informative prior*
	70	5.052	>0.999	>0.999	>0.999
75	30	1.732	0.739	0.669	0.912
	40	2.309	0.964	0.895	0.983
	50	2.887	0.998	0.981	0.998
	60	3.464	>0.999	0.998	>0.999
	70	4.041	>0.999	>0.999	>0.999

\*: The informative prior distribution on the treatment effect is based on estimates from a prior PAH study, in which analysis of change from baseline in 6 minute walk distance for 20 patients (7 controls, 13 treated) receiving oxygen for at least 12 hours a day yields an estimated treatment difference of 69.6 and pooled standard deviation estimate of 38.7.

#: Vague prior distribution which assumes no difference between groups.

All the sample size calculations were performed using EAST 6.4.

Using the above estimates yielded a planned sample size of 75 evaluable subjects per treatment arm (in total 150 subjects).

Further, in case the planned final analysis at N=150 (2 groups combined) is found not to have sufficient power, sample size increase could be made at IA up to a maximum of N=188 total patients (2 groups combined).

Assuming a 20% drop out rate, a total of 188 subjects (94 per treatment arm) are planned to support 150 at final analysis, with the ability to go up to 226 subjects (113 per treatment arm) to support 188 at final analysis, based on the sample size reassessment at the interim analysis.

As subjects must achieve a satisfactory adherence to the INOpulse delivery device, a dynamic randomization system will be used to ensure that approximately 94 (or 113) subjects per treatment cohort comply with the adherence criteria at Week 2. Enough subjects will be recruited such that a minimum sample size of 150 (or 188) subjects will complete 18 weeks of treatment on the INOpulse delivery device.

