## 5.5 Randomization and Blinding

### 5.5.1 Randomization

All eligible subjects will be screened for enrollment. All eligible and consented subjects will be randomized into 1 of 2 treatment groups in a ratio of 1:1. Randomization will be performed using an Interactive Response Technology (IRT) system.

Randomization will occur ONLY after the subject has signed the informed consent, has been enrolled into the study, and has met all Inclusion and Exclusion criteria. Study drug should be started after randomization during the Run-in visit.

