## 8.0 Interim Analysis

A formal interim analysis is planned in this study as follows:

1. Stop for futility (null hypothesis is accepted; there is no difference between iNO and Placebo).
2. Stop for efficacy (null hypothesis is rejected; there is difference between iNO and Placebo favoring iNO).
3. Sample size determination.
4. Stop in case of safety concerns. Safety concerns may be some imbalances in adverse events frequency which is not in favor of iNO. No formal statistical guideline is provided for this purpose, the sponsor relies on the medical expertise of DMC members.
5. Continue the trial with the planned sample size until next stage if point 1, 2 or 4 not apply.

The following two designs will define the interim analysis strategy:

- 1) Design 1: Groups Sequential Design (for efficacy part)
- 2) Design 2: Sample Size Re-estimation (SSR) (for futility and sample size re-estimation)

The interim analysis schedule planned as follows:

Schedule	Requirement
1 st	After 75 patients complete 18 Weeks of blinded treatment phase.
Final	After 150/188 (depending on CP and PP) patients complete 18 Weeks of blinded treatment phase.

Traditional group sequential design (GSD) alpha spending function  $\Gamma = -3$  ([Hwang, Shih, deCani, 1990](#)) is used to control the overall type 1 error at 0.025, 1-sided. The interim analysis rule ([Table 35](#)) is as follows.

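### If the primary test falls back to van Elteren, no rule covers a missing Week 18 walk: it becomes an observed-Week-18 comparison whose error can exceed nominal when missingness differs between arms

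*SAP*

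**What the plan says.** - **The fallback decides the trial.** Protocol 16.3.1: if normality is substantially violated, "the primary efficacy endpoint will be analyzed using the van Elteren test stratified by the prostanoid usage status". SAP 7.3.1 (Analysis of Non-Normal Data): "In case of normality issues, the analysis will be performed using van Elteren test for stratified response (change from baseline". The SAP code ranks one change value per subject within strata and has no visit term.
- **No imputation.** SAP 7.3.1: "Missing data will not be imputed for primary analysis". Protocol 16.3.5 and SAP 6.3 agree. The SAP change history gives the reason: the primary analysis is an MMRM.
- **Scores for deaths and withdrawals exist only in sensitivity analyses.** The zero-for-death, last-walk and worst-case rules (SAP 6.3; Table 24 nos. 3 to 6) are run as ANCOVA at Week 18 (Table 25). An MMRM on ranks (Table 24 no. 12) is also listed as a sensitivity analysis.
- **Planned drop-out.** SAP 5.4: "Assuming a 20% drop out rate, a total of 188 subjects (94 per treatment arm) are planned to support 150 at final analysis".
- **Follow-up off drug.** Protocol 10.1 and 11 encourage subjects who stop study drug to attend assessments through Week 18.
- **Timing of the choice.** SAP 7.3.1 (Normality Assumption) leaves the final choice of approach to model diagnostics after unblinding.

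**The concern.** Leaving missing walks unimputed is defensible for the MMRM. A subject who leaves after Week 10 still contributes the Week 6 and Week 10 walks, and the model is valid if missingness depends only on what was observed (MAR). A rank test of the Week 18 change cannot use those walks, so a subject without a Week 18 value leaves the test. The no-imputation rule thus carries over to a test for which its stated reason does not hold.

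If poor walkers are lost more often from iNO than from placebo, the iNO subjects who remain look better than those randomized, and the one-sided error rises. If they are lost more often from placebo, a real effect is partly hidden. Because the choice of test is settled after unblinding, an unwritten rule for missing walks would also be settled with the treatment codes known.

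**Working it through.** **1. The plan's own figures**
- Sample size: 150/(1 − 0.20) = 187.5, rounded up to 188; 75/0.80 = 93.75, rounded up to 94 per arm. If every planned drop-out missed Week 18, 0.20 × 188 = 37.6, about 38 subjects, would have no rank.
- Alpha: the Hwang-Shih-DeCani function with gamma −3 "is used to control the overall type 1 error at 0.025, 1-sided" (SAP 8.0). At half the information, 0.025 × (1 − e^1.5)/(1 − e^3) = 0.00456. The final nominal level is 0.02288. These match the stated 0.0046 and 0.0229.
- Power at 30 m, SD 75, fixed N = 150: 30/(75 × √(2/75)) = 2.449, and Φ(2.449 − 1.960) = 0.688. Simulating the design with sample size re-estimation gives 0.714 without futility, and 0.707 with futility when predictive power drives the rule. Protocol 16.2 states about 71%.

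**2. What enters the fallback**

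Van Elteren: T = Σ w_h [R_h − n_1h(n_h + 1)/2], with w_h = 1/(n_h + 1). R_h is the iNO rank sum in stratum h. The counts n_h and n_1h include only subjects with a Week 18 change; earlier walks appear nowhere.

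**3. Rejection with no effect, nominal one-sided 2.5%**

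From the plan: 94 per arm, 1:1, two strata. Assumed, not in the documents: equal strata, between-visit correlation 0.7, normal changes, and the drop-out mechanisms. The SD cancels under the null, and the interim look was not simulated. Van Elteren: 4,000 runs per row; MMRM (unstructured): 500 to 1,000. Slopes are log-odds per SD of the walk.

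| Missing Week 18 walk | van Elteren | MMRM |
|---|---|---|
| 20% per arm, random | 2.6% | 2.0% |
| Same dependence on last walk, same rate in both arms | 2.3% | 3.2% |
| Same dependence, 25% iNO / 15% placebo | 6.9% | 2.3% |
| Same dependence, 30% iNO / 10% placebo | 17% | 2.7% |
| 20% per arm; iNO after poor last walk (slope 1 / 1.5 / 3), placebo random | 12 / 18 / 28% | 2.5 / 2.0 / 3.4% |
| Reverse: placebo after poor last walk, iNO random | 0.1% | 2.3% |
| iNO only, dependent on the unseen walk (MNAR, slope 1 / 2) | 18 / 35% | 7 / 14% |
| Bounding case: iNO loses about its lowest 20% | 58% | 24% |

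Monte Carlo standard error for van Elteren: √(0.069 × 0.931/4000) = 0.4 points at 6.9%, and √(0.025 × 0.975/4000) = 0.25 points at 2.5%. For the MMRM at 2.5% it is 0.5 to 0.7 points, so 2.0% and 3.4% are compatible with nominal. With heavier-tailed changes (t, 5 df), the slope-1.5 case gave 15% instead of 18%.

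**4. Same question at the plan's final cut-off**

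Protocol 16.5: "It requires $p < 0.0229$ 1-sided for statistical significance". With that cut-off and correlation 0.8, the fallback rejects in 4.5 to 7.3% at 25% iNO versus 15% placebo, and in 2.3 to 2.6% at equal drop-out. In a run with a true 30 m effect and 15% iNO versus 25% placebo, power was 72% (SD 60) and 49% (SD 75). At equal 20% drop-out it was 85% and 67%, so the losses are 13 and 18 points.

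**5. Candidate rules**
- *Multiple imputation within arm under MAR, then van Elteren.* Z = mean(T_b)/√[mean(V_b) + (1 + 1/m)B], where T_b and V_b are the statistic and its variance in imputation b, B is the between-imputation variance, and m = 20 (1,500 runs). Null rejection: 2.5% (random, 20% per arm), 2.4% and 1.3% (iNO-only dependence, slopes 1.5 and 3), 3.2% (30% versus 10%). Power at 30 m, SD 75 with random drop-out: 71%, against 66% for observed cases. A separate run gave 1.7 to 2.9%, with power near 69 to 70%.
- *Deaths ranked lowest.* With 3 / 5 / 8 deaths on iNO and none on placebo: 1.4 / 1.4 / 0.6%, against 4.1 / 6.7 / 11.8% when deaths are dropped.
- *Every missing subject ranked lowest.* Still 8 to 16% when equal 20% rates hide different reasons; power falls to 39%.
- *Deaths and adverse-event withdrawals lowest, last walk carried forward for the rest.* About 5% under the null at 15% iNO versus 25% placebo (4.1 to 6.9% in one set of runs). Across runs it costs roughly 5 to 16 points of power at equal drop-out, and far more at 25% versus 15%.

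**The case against.** **The plan already looks at this.** Table 24 no. 12 is a rank-based MMRM that uses earlier walks, and four further ITT analyses score deaths as zero. They could expose a biased fallback. They stand as sensitivity analyses only and do not change the decisive test.

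**A fifth of the trial need not be missing.** A reader might infer that about 20% of subjects will have no Week 18 walk and that the test is completers-only. The documents do not support this. The 20% is a planning allowance, and walks made off drug at Week 18 count. This point stands in full: the accurate description is an observed-Week-18 test.

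**Inflation is conditional.** A reader might infer that the fallback generally favours iNO. It does not: with the same process in both arms it is near nominal, and in the reverse pattern it is conservative. The documents do not forecast drop-out by arm. SAP 2.0 reports 9 serious adverse events at 75 mcg/kg IBW/hr against 4 on placebo in Phase 2, while protocol 5.1 calls them balanced. Neither statement is a drop-out rate.

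**Deaths are not specific to the fallback.** The MMRM gives them no Week 18 score either. Under MNAR the MMRM inflates too, so only the excess over it belongs to the fallback.

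**Imputation was taken out of the primary analysis on purpose**, following FDA recommendations and Amendment 3. That is a good reason not to bring last-value-carried-forward back. It does not settle the fallback, since the recorded reason refers to the MMRM.

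**Conclusion.** The gap is real. If the fallback is used as written, the ITT primary test compares only subjects with a Week 18 walk, and the one-sided error can exceed nominal when missingness depends on walking ability and differs between arms in rate or reason. The size is about 4.5 to 7% at 25% iNO versus 15% placebo, and up to about 17% at 30% versus 10%. The rows with equal rates but different reasons go higher, but they are stylized contrasts.

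All these sizes rest on assumed drop-out mechanisms and correlations of 0.7 to 0.8, on a single look, and mostly on normal changes. The fallback applies only when normality fails, and the one heavy-tailed run pointed the same way. The text gap does not depend on these assumptions.

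Ranking adverse-event withdrawals lowest and carrying the last walk forward might look like the natural remedy, since it mirrors SAP 6.3 item 1. It should not be the primary fallback: it inflates error in the reverse pattern and costs considerable power. It also turns the test into a mixture of walking and tolerability.

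**What to change.** Before unblinding, add to SAP 7.3.1 and protocol 16.3.1: if the van Elteren test is used, missing Week 18 changes are multiply imputed within arm under MAR from baseline 6MWD, prostanoid stratum and the Week 6 to 14 walks, and the van Elteren statistics are combined across imputations. State the imputation model and the number of imputations.

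An acceptable alternative is to make the ranked MMRM of Table 24 no. 12 the fallback. Its trigger would need aligning, because that row requires violations of both normality and homogeneity of variance. Its error rate was not simulated here.

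Keep two sensitivity analyses: the observed-case van Elteren test, and a version with deaths ranked lowest.

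Cost: a short paragraph in each document, a little more programming and no new data. The test would then rest on the same MAR assumption as the planned MMRM and would not protect against MNAR drop-out. The imputation was checked only on normal data, so the chosen model should be tried on skewed or heavy-tailed changes before it is fixed.
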